## 5. Inclusion/Exclusion Criteria

### *Inclusion Criteria:*

- 1. Adults ( $\geq 18$  years) presenting with neurological symptoms due to acute ischemic stroke (onset within the week).
- 2. Evidence on brain MRI of acute ischemic stroke (imaging negative strokes and TIAs will be excluded).
- 3. Native English speaker (by self-report) prior to stroke.
- 4. NIHSS  $<8$  at initial follow-up visit ( $\sim 30$  days post).
- 5. mRS 0-2 at initial follow-up visit.

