## 1. Abstract

Thrombectomy has significantly improved stroke outcomes. Nearly 80% of our clinic population now present with small strokes and low NIH Stroke Scale (NIHSS) scores. However, despite “good recoveries”, greater than 40% endorse significant problems with higher-level cognitive functions, mood disorders, and fatigue. The natural history and pathophysiology of these deficits are not as well described as motor or language deficits; but they are equally debilitating, preventing previously high-functioning active individuals from returning to their prior workplace and social environments. This can be particularly difficult for the elderly, resulting in early retirement and loss of independence. The pathophysiology underlying these deficits remains unclear. Impairments in executive function and processing speed occur independent of stroke size, location, or depression. Using magnetoencephalography (MEG), a tool able to evaluate neurophysiologic processes in real time akin to EEG with better spatial resolution, *we have found that cerebral activation patterns are slowed and more diffuse during task completion in stroke patients compared to controls*; and at rest there is **abnormal activity in the frontal lobes**, an area critical for executive function, processing speed, affect regulation, and decision making. Some patients improve over months; however, recovery is variable and by this time many have made critical life decisions. There is little data regarding effective treatment options. The ability to hasten improvement would significantly improve morbidity in a group with excellent recovery potential.

Mindfulness has been practiced since ancient times, but only recently gained popularity as an effective treatment for anxiety and depression both in normal individuals and those with chronic disease states. Mindfulness Based Stress Reduction (MBSR) has also been evaluated in a small series of patients with chronic stroke and traumatic brain injury and has *shown to improve performance during tasks of executive function*. A combination of meditation, body awareness, and yoga, MBSR is an active process thought to engage the frontal lobes. Based on our current understanding of pathophysiology, MBSR may serve as an attractive non-pharmacologic intervention to improve *subacute* post-stroke mood and cognitive dysfunction.

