We will recruit a cohort of patients with minor stroke (NIHSS <8, modified Rankin score 0-2). Following baseline assessment of depression, fatigue, cognition, functional status, and patient satisfaction, individuals will be randomized to a standard 8 week MBSR course aimed at improving attention and concentration, and reducing anxiety and depression, or a bi-monthly standard Stroke Support Group (SSG). All patients will undergo reassessment post-intervention (~4-6 months post-infarct), along with MEG pre- and post-intervention. Participants will undergo neuroimaging pre- and post-intervention. We will evaluate differences in activation patterns and functional connectivity both at rest and during a visual cognitive task. We hypothesize that both groups will initially exhibit abnormal frontal lobe function compared to controls; however, after MBSR this will improve versus the SSG group.

Participants will also be administered a pre- and post-intervention Montreal Cognitive Assessment (MoCA), along with a battery of cognitive tasks to measure attention, concentration, processing speed, and executive function. Performance will be compared pre- and post-intervention, and for MBSR versus SSG participants. We hypothesize scores will be significantly better following MBSR compared to the SSG group. Finally, the PHQ9 and other measures of patient-reported outcomes (eg., mood) will be given to patients pre- and post-intervention and compared across groups at each time point. We hypothesize MBSR will improve rates of depression/anxiety compared to SSG. We will also evaluate patient satisfaction scores, measures of functional recovery: the modified Rankin scale (mRS) and Barthel Index (BI), and the likelihood of successful return to work. Individuals with minor stroke have tremendous potential to return to their baseline level of function, though often struggle. If effective in reducing post stroke mood and cognitive disorders for those with minor stroke, allowing them to return to work, MBSR will significantly reduce post-stroke morbidity and improve quality of life.

---

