**Objective 2: To determine the impact of mindfulness training on post-stroke cognitive impairment.**

Participants will be administered a pre- and post-intervention Montreal Cognitive Assessment (MoCA), along with a battery of cognitive tasks to measure attention, concentration, processing speed, and executive function. Performance will be compared pre- and post-intervention, and for MBSR versus SSG participants.

**Objective 3: To determine the impact of mindfulness training on post-stroke depression.** The PHQ9 will be given to patients pre- and post-intervention and compared across groups at each time point.

*As secondary objectives we will also evaluate patient satisfaction scores, measures of functional recovery: the modified Rankin scale (mRS) and Barthel Index (BI), and the likelihood of successful return to work.*

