### 3. Background

Stroke is common, affecting nearly 800,000 individuals in the United States each year. It is debilitating, the leading cause of long-term disability and 4th leading cause of death. It is costly, resulting in an average of \$36.5 billion dollars in healthcare expenditures and lost wages annually. Advances in treatment (intravenous tissue plasminogen activator and mechanical thrombectomy) have significantly reduced motor and language deficits, converting large hemispheric lesions into smaller infarcts with better overall long-term outcomes. Unfortunately, many patients arrive to the hospital too late to benefit from acute treatment, or continue to have symptoms despite intervention. Within our patient population, nearly 80% of individuals presenting for follow-up 4-6 weeks post-stroke report only “minor symptoms”, with low severity measured by NIH Stroke Scale (NIHSS) and modified Rankin scores (mRS). Though these individuals lack dense hemiparesis or aphasia; over half endorse some degree of cognitive impairment, mood disorder, or fatigue that significantly impacts recovery. These symptoms appear independent of stroke size, location, or depression.

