### *Exclusion Criteria:*

- 1. Primary intracerebral hemorrhage- blood on imaging.
- 2. Presence of proximal large vessel occlusion.
- 3. Cortical exam findings including aphasia or neglect.
- 4. Prior history of dementia or undertreated psychiatric illness.
- 5. Uncorrected hearing or visual loss.
- 6. Inability to attend weekly MBSR or support group sessions.
- 7. Inability to travel to College Park, Maryland for 2 MEG recording sessions
- 8. Presence of any of the following that would lead to significant artifact on MEG: cardiac pacemaker, intracranial clips, metal implants or external clips within 10mm of the head.
- 9. Claustrophobia, obesity, and/or any other reason leading to difficulty staying in the MEG machine.

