**To determine the impact of mindfulness on post-stroke depression:**

- Participants will be administered the PHQ-9 pre- and post-intervention. Paired t-tests will be used to evaluate for significant differences in scores between time points using each score as a continuous variable. Chi square analysis will be used to evaluate presence or absence of moderate depression (PHQ9 score >9). Independent t-tests and chi square analysis will compare scores of MBSR versus SSG participants for each time point.
- *Sample Size.* Based on prior MBSR studies, we anticipate that this will show a greater clinical effect than change in MoCA, giving us more than adequate power to detect differences with this sample size.

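### Objectives 2 and 3 target cognitive impairment and depression, but entry requires neither, and the between-arm comparisons of MoCA and PHQ-9 make no planned use of the baseline scores

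*Combined protocol and SAP*

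**What the plan says.** The document is the combined protocol and SAP.

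- **Aims.** Section 2 gives Objective 2 as "To determine the impact of mindfulness training on post-stroke cognitive impairment" and Objective 3 as "To determine the impact of mindfulness training on post-stroke depression".
- **Entry.** The five inclusion criteria in section 5 cover age, MRI-confirmed ischaemic stroke, native English, NIHSS below 8 and "mRS 0-2 at initial follow-up visit". None asks for a cognitive, mood or fatigue deficit. The nearest criterion is an exclusion: "Prior history of dementia or undertreated psychiatric illness".
- **How common the problems are.** The Abstract says that "greater than 40% endorse significant problems with higher-level cognitive functions, mood disorders, and fatigue". The Background says that "over half endorse some degree of cognitive impairment, mood disorder, or fatigue that significantly impacts recovery".
- **Order of events.** The Abstract states: "Following baseline assessment of depression, fatigue, cognition, functional status, and patient satisfaction, individuals will be randomized to a standard 8 week MBSR course". Baseline mood and cognition are therefore known before allocation. Neither the Abstract nor section 4 describes a randomisation method or any stratification.
- **Analysis.** For cognition, section 7 plans t-tests and chi-square tests with a MoCA cut-off of 26, within arm over time and between arms at each time point. For depression it treats PHQ-9 as continuous and adds: "Chi square analysis will be used to evaluate presence or absence of moderate depression (PHQ9 score >9"). ANCOVA is named for the MEG outcomes but not for MoCA or PHQ-9.
- **Adjustment.** Section 7c provides multivariable linear regression if confounders turn out to be unevenly distributed. The examples cover participation, demographics, education, antidepressants and comorbidity. Baseline MoCA and baseline PHQ-9 are not among them.

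**The concern.** The objectives name conditions that an unknown share of participants will not have at entry. On the binary analyses, someone who starts on the unimpaired side of a cut-off cannot recover across it. On the continuous scores, that person has less room to gain. A post-intervention comparison that ignores the starting point mixes any treatment effect with whoever happened to be impaired at entry.

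Two things are at stake. The first is precision: at 20 per arm, chance differences in baseline status can be as large as a worthwhile effect, and the plan leaves unused the data that would remove much of this noise. The second is interpretation: a null result in a mixed population would not show that MBSR fails to help patients who are depressed or cognitively impaired. The Sample Size paragraph in section 7 intends the estimates to inform a larger trial, so both matter beyond this study.

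**Working it through.** **The plan's own figure.** The only sample-size figure is at least 20 per group. It cannot be reproduced, because no alpha, power, effect size, SD, event rate or dropout is given. The claim of more than adequate power for PHQ-9 also comes without a number. The checks below take 20 per arm as given and, where a test is involved, assume two-sided alpha 0.05 and 1:1 allocation.

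**1. Chance imbalance in baseline impairment.**

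Inputs: 20 per arm (section 7); share impaired p = 0.3 to 0.5. The share is an assumption. The documents' figures of over 40% and over half suggest the region but do not measure it. Simple randomisation is assumed, because no other method is described.

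Let X1 and X2 be the impaired counts in the two arms, independent Binomial(20, p). The probability of a gap of at least 4 of 20 (20 percentage points) is the sum of P(X1 = i) × P(X2 = j) over all |i − j| ≥ 4.

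| Assumed share impaired | P(gap ≥ 4 of 20) |
|---|---|
| 0.2 | 0.164 |
| 0.3 | 0.226 |
| 0.4 | 0.258 |
| 0.5 | 0.268 |

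The row at 0.2 is a lower assumption, for one domain alone. If the total impaired is instead fixed (16 or 20 of 40) and split at random, the probability is 0.333 or 0.343. For the continuous scores, the between-arm difference in baseline means has standard error √(2/20) = 0.316 SD, so a difference of at least 0.4 SD has probability 2 × [1 − Φ(0.4/0.316)] = 0.21.

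**2. How large that is against an effect.** Suppose 40% of SSG participants are impaired after the intervention and MBSR halves this to 20%. The effect is 40 − 20 = 20 percentage points, the same size as the gap in step 1. Power for this comparison at 20 per arm is 28%, and 80% power needs 82 per arm. For 50% against 25%, power is 37% and 58 per arm are needed. The unadjusted binary comparison is thus already weak, and variation in starting status is part of its noise.

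**3. A limiting case for the mixed population.** Assume an effect d in impaired participants, none in the others, and a common SD. The average effect is then f × d, where f is the impaired share. The difference detectable with 80% power at 20 per arm is (1.960 + 0.842) × √(2/20) = 0.886 SD.

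- f = 0.5: 0.5 × 0.886 = 0.443; power 29%; 80 per arm needed for 80%.
- f = 0.4: 0.4 × 0.886 = 0.354; power 20%; 125 per arm needed for 80%.

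This is an extreme, not an estimate, because the zero effect in unimpaired participants is an assumption that the documents do not make.

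**4. What section 7c repairs.** Its regression depends on seeing imbalance, so baseline adjustment is not assured. It names neither baseline score. Being linear, it does not replace the chi-square tests. ANCOVA on the baseline score has a residual variance of about (1 − ρ²) times that of the unadjusted comparison, where ρ is the correlation between baseline and follow-up scores. This gain is available whether or not imbalance appears. The documents give no value for ρ.

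**The case against.** Unselected entry is a defensible choice for a pilot. MEG comes first among the primary outcomes, both arms are expected to show abnormal frontal activity at baseline, and section 7 concedes that power may be inadequate. An impairment threshold would slow recruitment: at 40-50% impaired, finding 40 impaired patients means screening 40/0.4 = 100 to 40/0.5 = 80 otherwise eligible patients. This stands, and no threshold is asked for here.

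Section 7c also gives partial protection. Its covariate list is only illustrative, and comparing the arms at baseline would reveal a gap. That softens the point, but adjustment remains conditional and the relevant covariates unnamed.

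Several stronger readings are tempting, and the documents do not support them:

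- *Unimpaired participants cannot improve.* This holds only for the binary analyses. MoCA, the global and individual cognitive scores and PHQ-9 are also compared as scores, on which such participants can still gain.
- *An unimpaired participant is an automatic success.* That person can worsen across the cut-off by follow-up, and the post-intervention chi-square counts it. Dropping these participants would discard that information.
- *mRS 0 means symptom-free in cognition and mood.* The Background argues that these deficits are easily missed in patients with good recoveries. The missing MoCA or PHQ-9 criterion is the evidence, not the mRS range.
- *About half of entrants have nothing to treat.* The two prevalence figures are self-reported lower bounds from the clinic population, for a composite that includes fatigue. They are not rates of MoCA below 26 or PHQ-9 above 9 among those enrolled. The true shares could lie either way, so the 0.4-0.5 multiplier in step 3 is illustrative only.
- *Randomisation ignores baseline impairment by design.* The plan is silent on method; absence of stratification is inferred from that silence.
- *Exclusion 4 removes the very patients Objective 3 concerns.* The reference to prior history most naturally covers both dementia and psychiatric illness. At most this needs a clarifying phrase.

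**Conclusion.** The concern holds in a limited form. Entry does not require the conditions named in Objectives 2 and 3, and the between-arm analyses of MoCA and PHQ-9 have no assured adjustment for scores collected before allocation. Post-intervention rates on the two cut-offs will partly reflect status at entry.

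The size that can be defended is the imbalance figure: a 23-27% chance that impaired counts differ by 4 or more of 20, under simple randomisation, 20 per arm and an assumed 30-50% impaired. A reader might infer from this that the comparison is biased. It is not: the gap can go in either direction, and valid tests already allow for it. The cost is lost precision, together with a conclusion that would not match the population studied. The dilution figures show how low power could fall in an extreme case and are not a forecast.

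**What to change.** 1. Pre-specify the MBSR v SSG comparison of post-intervention MoCA, cognitive scores and PHQ-9 as ANCOVA on the matching baseline score, for all randomised and regardless of observed imbalance. This does most of the work.
2. Stratify the randomisation list on baseline impairment (MoCA <26 or PHQ-9 >9) and include that stratum in the model. The composite stratum does not balance cognition and depression separately, so it supplements item 1 and does not replace it.
3. Keep the binary comparisons in all participants, adjusted for baseline status on the same cut-off. Report recovery among those impaired at baseline as descriptive only: at 40% impaired this is about 0.4 × 20 = 8 per arm, and possibly fewer for depression alone.
4. Word the conclusion as the effect on cognitive scores and depressive symptoms in unselected minor stroke.

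The cost is a two-stratum list, scoring MoCA and PHQ-9 before allocation, and slightly more analysis work. No extra patients or assessments are needed.

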### *Exclusion Criteria:*

- 1. Primary intracerebral hemorrhage- blood on imaging.
- 2. Presence of proximal large vessel occlusion.
- 3. Cortical exam findings including aphasia or neglect.
- 4. Prior history of dementia or undertreated psychiatric illness.
- 5. Uncorrected hearing or visual loss.
- 6. Inability to attend weekly MBSR or support group sessions.
- 7. Inability to travel to College Park, Maryland for 2 MEG recording sessions
- 8. Presence of any of the following that would lead to significant artifact on MEG: cardiac pacemaker, intracranial clips, metal implants or external clips within 10mm of the head.
- 9. Claustrophobia, obesity, and/or any other reason leading to difficulty staying in the MEG machine.

## 6. Drugs/ Substances/ Devices

- a. No drugs or substances will be administered.
- b. We will be using magnetoencephalography (MEG), as above.

## 7. Study Statistics

- a. Primary outcome variables include: MEG- changes in spectral properties and an estimate of the localization of spontaneous brain activity during resting state, functional connectivity during resting state. Clinical- performance on the MOCA and other cognitive measures (as part of the Recovery Study), patient-reported outcomes: fatigue, depression, satisfaction, quality of life.
- b. Secondary outcome variables include: changes in spectral properties, spontaneous brain activity, and functional connectivity during completion of various cognitive tasks.
- c. We will use an intention-to-treat analysis; however, we will adjust for degree of participation and consider an additional exploratory per-protocol analysis. For those lost-to-follow-up, data will be censored at the time they are lost. In addition to the proposed analyses, if there is evidence for an uneven distribution of confounding factors across treatment and control groups, we will perform multivariable linear regression to adjust for confounders (eg. degree of participation, age, sex, level of education, antidepressant use, and major medical co-morbidities (Charlson Comorbidity Index)).

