## 2. Objectives

Objective 1: To determine the effect of MBSR on abnormal cerebral activation patterns on MEG after stroke. Participants will undergo neuroimaging pre- and post-intervention. We will evaluate differences in activation patterns both at rest and during a visual cognitive task using cluster-based permutation tests. Patients in the MBSR and SSG groups will be compared to one another and to patients with no infarct

(previously collected cohort). T-tests and ANCOVA will be used to determine differences between groups at each time point. Functional connectivity studies will also be performed to evaluate differences between groups.

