**To determine the effect of MBSR on abnormal cerebral activation patterns on MEG after stroke:**

- Participants will undergo neuroimaging at 1 and 6 months post-stroke. Participants in the MBSR and SSG will be compared to a previously collected group of controls with no infarct. Source localized whole brain activation will be assessed to determine overall differences in space and time between each group (MBSR v SSG) versus controls for each time point. Cluster-based permutation tests (based on independent measures t values) will then be performed to evaluate mean differences in activation for ROIs between groups at each time point. Paired t values will allow for evaluation of changes over time within each group. Amplitude of peak activation and spike latency will be assessed. ANCOVA will allow for adjustment of potential confounders.
- *Sample Size.* We have been able to demonstrate results at or approaching statistical significance for our current cohort of patients with minor stroke versus controls after enrolling only 9 participants. This number is similar to many other published studies evaluating differences in activation patterns on MEG. We do anticipate less of a difference when comparing stroke patients to other stroke patients, and will therefore increase our sample size to at least 20 individuals in each group. There remains a chance given the potential for improvement in both groups, that we may still be inadequately powered to detect long-term outcomes in this pilot study; however results will also allow treatment effect estimates that will inform a larger clinical trial.

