**To determine the impact of mindfulness on post-stroke cognitive impairment:**

- The MoCA and cognitive battery will be administered at 1 and 6 months post-stroke. T-tests and chi square analysis will compare cognitive performance (MoCA, global cognitive score, and individual cognitive tests) pre- and post-intervention for each group (MoCA cutoff <26), and MBSR v SSG participants at each time point.

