**To determine the functional significance of the treatment, patient perception and satisfaction with recovery**

- Along with degree of successful reintegration will be evaluated using Likert scores. Regression models will be created to evaluate the effect of mindfulness on perception of recovery and patient satisfaction at each time point. Within regression models, we will include traditional markers of recovery (mRS and BI) to determine the independent effect of mindfulness training on satisfaction and quality of life.

d. Early stopping rules: the study will be stopped if the participant is unable to tolerate the MEG or MBSR.

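### Section 7a names eight or nine unranked primary outcomes with no error control across them, and this pilot does not label their tests exploratory

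*Combined protocol and SAP*

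**What the plan says.** Section 7a opens the list with "Primary outcome variables include: MEG- changes in spectral properties and an estimate of the localization of spontaneous brain activity during resting state, functional connectivity" at rest, and continues with "Clinical- performance on the MOCA and other cognitive measures (as part of the Recovery Study), patient-reported outcomes: fatigue, depression, satisfaction, quality of life". The verb leaves the list open, and nothing in it is ranked.

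The methods differ by outcome:

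- **MEG.** Under Objective 1 in section 2, "T-tests and ANCOVA will be used to determine differences between groups at each time point". The MEG part of section 7 adds cluster-based permutation tests, which "will then be performed to evaluate mean differences in activation for ROIs between groups at each time point".
- **Cognition.** "T-tests and chi square analysis will compare cognitive performance (MoCA, global cognitive score, and individual cognitive tests"), before and after intervention within each group and between arms at each time point.
- **Depression.** Section 7 tests PHQ-9 as a continuous score and as a dichotomy (above 9), between arms at each time point.
- **Satisfaction.** "Regression models will be created to evaluate the effect of mindfulness on perception of recovery and patient satisfaction at each time point". In section 2, however, its status is different: "As secondary objectives we will also evaluate patient satisfaction scores".
- **Fatigue.** No test is named.

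On the aim of the study, section 4c and the MEG sample-size paragraph of section 7 call it a pilot. That paragraph admits that power may be inadequate and says the results will also provide effect estimates for a larger trial. The abstract hypothesises significantly better cognitive scores with MBSR, and the depression sample-size paragraph claims more than adequate power. The word exploratory appears once, in section 7c: the investigators will "consider an additional exploratory per-protocol analysis".

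**The concern.** Outcomes that are all primary and all equal leave open which result answers the trial's question. No passage gives an alpha, a ranking or a procedure for handling several primary outcomes together. Whichever outcome crosses p<0.05 could then be reported as a primary finding.

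The practical stake is the next trial. Section 7 says the estimates will inform it, and an outcome picked because it was the one that reached significance is a poor basis for choosing an endpoint. The effect estimate behind such a choice also tends to be too large. The two statuses of satisfaction show that the hierarchy is unsettled even within the document.

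**Working it through.** **1. The plan's own figure.** The only design figure is at least 20 per group. It cannot be reproduced, because no alpha, power, effect size or SD comes with it. It rests on an earlier comparison with controls after 9 participants.

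**2. Counting the primary outcomes in section 7a.**

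- MEG: spectral properties, localization of resting activity, resting connectivity. That is 3, or 2 if the first two are read as one.
- Clinical: MoCA, other cognitive measures, fatigue, depression, satisfaction, quality of life. That is 6.
- Total: 3 + 6 = 9, or 2 + 6 = 8. Both are minimum counts, since the other cognitive measures are plural and section 7 splits them into a global score and individual tests.

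**3. Looking for error control.** Cluster-based permutation normally limits error over the many locations and times within one MEG comparison. It does not act across the MEG measures, and it does not reach MoCA, PHQ-9, fatigue, satisfaction or quality of life. Nothing else in the documents serves this purpose.

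**4. Illustrative false-positive rates.** Assumptions, none of them in the documents: one two-sided 0.05 between-arm test per outcome, no true effect, and equal pairwise correlation. For m independent outcomes the chance of at least one false positive is 1 - 0.95^m. Correlated cases come from simulating m equicorrelated normal test statistics (1,000,000 draws).

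| Outcomes | Independent | Corr. 0.3 | Corr. 0.5 | Corr. 0.7 |
|---|---|---|---|---|
| 3 (one per objective) | 14.3% | 13.6% | 12.6% | 11.0% |
| 8 | 33.7% | 29.9% | 25.1% | 19.1% |
| 9 | 37.0% | 32.6% | 26.9% | 20.3% |

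**5. Power cost of a Holm correction across three outcomes.** Noncentral t with n = 20 per arm, 38 degrees of freedom and noncentrality d × √(20/2). The first Holm step tests at 0.05/3 = 0.0167, so its power is a lower bound for Holm. The effect sizes are assumed.

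| Effect (SD) | Power at 0.05 | Power at 0.0167 |
|---|---|---|
| 0.5 | 34% | 19% |
| 0.8 | 69% | 52% |
| 1.0 | 87% | 74% |

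**6. Value of adjusting for baseline.** Simulated ANCOVA (40,000 trials), 20 per arm, assumed 0.8 SD effect, two-sided 0.05. Power is 68% if the baseline/follow-up correlation is 0, 73% at 0.3, 80% at 0.5 and 92% at 0.7. The unadjusted t-test gives 69%.

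The figures in steps 5 and 6 do not describe a cluster-permutation MEG test.

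**The case against.** The best defence is that this is a pilot with three separate questions. Sections 1 and 2 set out MEG, cognition and depression as distinct objectives, each with its own hypothesis. Whether error must be controlled across distinct questions in a pilot is partly a matter of judgement. The plan says it may be underpowered, and a false lead would normally be tested in the larger trial. A hypothesis of significant improvement in an abstract is not a decision rule. Much of this stands: it is why the three-outcome rate belongs beside the others, and why a formal correction is optional here.

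It does not remove the point. Effect estimation is added to the testing and does not replace it. Using the word exploratory for the per-protocol analysis alone implies that the remaining analyses are something else. Reading by objective does not give one test per question either, because cognition has MoCA, a global score and individual tests, and PHQ-9 is tested in two forms.

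Three stronger readings are tempting, and the documents do not support them:

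- **That the plan declares success if any one primary is significant.** No passage states such a rule.
- **That there is no error control at all.** Cluster-based permutation provides some within a MEG comparison. The gap is across outcomes.
- **That section 7a defines the clinical outcomes as changes from baseline.** The word changes there belongs to the MEG items. The case for baseline adjustment rests on precision.

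**Conclusion.** The concern holds as a defect in how the plan ranks and labels its outcomes: eight or nine equal primaries, no alpha or error control across them, two statuses for satisfaction, and tests not labelled exploratory. It should be corrected, but it does not invalidate the trial.

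Under the stated assumptions, the chance of at least one false positive is roughly 19-33% for eight or nine outcomes at correlations of 0.7 to 0.3, and 34-37% if they are independent. A reader might take these as the plan's actual error rate. They are not: the documents give no alpha or correlations, MEG activation uses permutation tests, satisfaction uses regression, and fatigue has no named test. The count of outcomes and the missing hierarchy need none of these assumptions.

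**What to change.** Choose one of two routes.

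1. **Single primary.** Name one outcome per objective: one pre-specified resting-state MEG measure with its test, MoCA or the global cognitive score, and PHQ-9. Make one of the three the primary and state its alpha. The pandemic section allows scanning to stop, with cognitive outcomes used alone in the participants affected. So either choose the cognitive outcome or PHQ-9 as primary, or state how missing MEG data are handled. Report all other outcomes as secondary or exploratory, as MBSR versus SSG estimates with 95% confidence intervals.
2. **Exploratory pilot.** State that all outcomes are exploratory, that they are reported as estimates with 95% confidence intervals, and that no efficacy conclusion rests on any single p-value.

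Under either route:

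- Make the main clinical comparison MBSR versus SSG after the intervention, adjusted by ANCOVA for the baseline value already collected, in place of separate t-tests at each time point. Section 7c's confounder adjustment is conditional on imbalance, and its examples do not include the baseline outcome value.
- Make sections 2 and 7 agree on the status of satisfaction.

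The change is to wording and needs no new data. A single primary or the exploratory label costs no power for that comparison. Baseline adjustment gains power unless the baseline/follow-up correlation is close to zero, where the loss is about one percentage point (69% to 68% in the working). Holm across the three outcomes is an optional alternative to a single primary, at the power cost tabulated above. For a pilot of this size that is a real trade-off.
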